5.4 INELIGIBLE AND NON-RECRUITED PARTICIPANTS

Ineligible individuals will be thanked for their interest in the study and will take no further part.

5.5 RANDOMISATION

5.5.1 Randomisation

Not required.

5.5.2 Intervention Allocation

Not required

5.5.3 Withdrawal procedures

Participants will be informed that they are free to withdraw from the study at any time. We will request that any data collected up until the point of withdrawal be included for analysis. Participants will not be replaced.

6 DATA COLLECTION & MANAGEMENT

6.1 DATA COLLECTION

Due to current social distancing guidelines, it is likely that study appointments will be conducted remotely, for example by voice or video call. This is likely to mirror the way in

V3 31-08-2020

which the Tayside Pain Service operates its clinical activity. If risks of COVID infection can be minimised and depending on prevailing guidelines, appointments may be conducted face to face either in the clinical research facility (CRF) at Ninewells Hospital, Dundee or at participants' homes.

6.1.1 Qualitative analysis

Following consent, the first study appointment will be arranged. Semi structured interviews of participants will be conducted by the study researcher, who will be trained in qualitative research. Interviews, which will last approximately one hour, will be recorded onto encrypted digital media and guided by a topic guide. Audio recordings will be transferred from the encrypted recorders onto the University of Dundee secure network using a password-protected University of Dundee computer. Following transfer, the audio file will be removed from the encrypted digital recorder. Audio files will be identified using the participant unique study ID. The key that links this study ID number to the identity of the participant will be stored securely on a University of Dundee computer for study management purposes. Audio files will then be transcribed by the study researcher. It is possible that the interviewee may compromise their identity or those of others during the interview process. In this case, the transcriber will assign non-identifiable labels (e.g. interviewee 1) to the participant.

Interviews with stakeholders will be carried out by the study researcher and these are also likely to be done remotely via voice or video call. It is possible that they may be carried out at convenient, private locations e.g. at the stakeholders' place of work, or at the CRF, Ninewells, if more convenient, dependent on the prevailing risk of COVID infection.

6.1.2 Quantitative analysis

6.1.2.1 Validated questionnaires

Validated questionnaires will be completed by participants at study appointments 1 and 2: Brief Pain Inventory, Depression, Anxiety and Stress Scale, Pain Self-Efficacy Questionnaire (PSEQ);Pain Catastrophising Scale (PCS); Tampa Scale of Kinesiophobia and International Physical Activity Questionnaire (short form, last 7 days), The Physical Activity Stages of Change Questionnaire. Participants will receive paper copies of the questionnaires in their delivery with the activity monitor/s. The participant will then have the choice to fill out the paper copy of the questionnaire or have the questions read out loud by the researcher. Participant's preference will be discussed with a member of the study team prior to the participant's first appointment. Data will then be collected either by a paper copy of the questionnaire which can be returned to the study team by provided freepost or by the interviewer reading out the questionnaire and recording the answer by completing the paper questionnaires. Questionnaire data will then be entered into an electronic data management system (Excel) held on University of Dundee server. Analysis will be carried out using SPSS or equivalent statistical software.

6.1.2.2 Fitness tracker data

Participants will be instructed on how to fit the activPAL monitor at study appointment 1 and advised to wear this continuously for seven days. At the second, remote study appointment they will be instructed how to remove the trackers and how to return them to the study team They will be given an instruction leaflet on how to fit, use and remove the activPAL trackers. Trackers will either be collected and returned to the study team by courier or collected by a member of the study team, while observing social distancing guidelines. The data from the activPAL trackers will be downloaded onto University of Dundee servers where it will be identified using a study ID number. ActivPAL data will be analysed using an event-based

V3 31-08-2020

approach (assessing continuous periods of a single activity, e.g. walking) to allow an assessment of the quantity, pattern and timing of actual physical activity (20). Derived outcome measures will include, time spent sitting, standing and walking and time spent walking at a moderate intensity.

20 participants will also be asked to wear a Fitbit. The study team will create individual Fitbit accounts for each of these participants. These accounts will not use the individuals' real names, and will be linked to email accounts generated by the University of Dundee IT. Participants' date of birth, gender, height and weight will be entered into the accounts. Location service will be disabled on the Fitbit account. Fitbit have agreed to a take over by Google, and terms of this agreement are likely to be settled in 2020. At the moment we cannot be sure what the implications of this agreement will be. Both companies have issued statements that they will respect existing policies on data storage and sharing. Since some people may not be in agreement with sharing their data with multinational companies such as Fitbit or Google, we will provide the option to consent to wearing the ActivPAL only. Data from FitBit monitors will be downloaded from the individual accounts opened for each participant. Important data will be the number of steps, but will also include recorded daily distance walked, flights of stairs climbed and periods of prolonged activity. These data will be extracted from the Fitbit accounts of individual accounts into Excel spreadsheets. Data will be saved in an anonymised format using study ID.

Participants will be asked to complete a short questionnaire at appointment 2 to assess acceptability of wearing the trackers. Questionnaires will be read out to the participant and their responses recorded in the paper questionnaire by the researcher.

6.2 DATA MANAGEMENT SYSTEM

Data management will be conducted in compliance with TASC SOPs on Data Management, including TASC SOP53 Data Management Systems in Clinical Research.

The data management system (DMS) will be Excel, as approved by Sponsor and with guidance from the study statistician. Data collected on the ActivPAL fitness trackers will be analysed by collaborators at Glasgow Caledonian University. Anonymised data will be shared and analysed. The DMS will be based on the protocol and CRF for the study and individual requirements of the investigators. The CRF will collect only information that is required to meet the aims of the study and to ensure the eligibility and safety of the participant. The study database will be compliant with TASC SOP53 Data Management Systems in Clinical Research.

The database is managed in line with all applicable principles of medical confidentiality and data laws. The Data Controller will be the University of Dundee and the Data Custodian will be CI.

The PI may delegate CRF completion but is responsible for completeness, plausibility and consistency of the CRF. Any queries will be resolved by the PI or delegated member of the study team.

Database lock will be conducted in compliance with TASC SOP32 Locking Clinical Study Databases.

V3 31-08-2020

7 STATISTICS AND DATA ANALYSIS

7.1 SAMPLE SIZE CALCULATION

No formal sample size calculation was made for this exploratory study. We are aiming for a total of 40 patients completing the first study appointment. While we do not anticipate a high dropout rate from participants who have actively expressed an interest in taking part, there may be unforeseen circumstances that prevent study appointments being conducted, even after an appointment has been agreed. The non-attendance rate at routine clinic appointments is 12-15%, so we have extrapolated this to allow for up to an additional 5 patients being approached/ appointed (ie a total of 45, or 40 patients, whichever is reached sooner).

7.2 PROPOSED ANALYSES

Specific analyses will be detailed in the study statistical analysis plan which will be finalised prior to datalock.

7.2.1 Qualitative Analysis

Recordings of the semi-structured interviews will be analysed using framework analysis.

7.2.2 Quantitative analysis

7.2.2.1 Fitness tracker

An assessment of the level of PA undertaken by each participant will be made by analysing the variables, which include:

Feasibility outcomes: Number of days worn; Reported problems with wearing the monitor; Reported pain or discomfort while wearing the monitor; Reported duration and reasons for removing the monitor early (activPAL) or not wearing the monitor (FitBit).

Primary physical activity outcomes that are comparable between monitors:

Number of steps taken; Time spent in MVPA (moderate to vigorous physical activity). [For the activPAL this will be assessed as the time spent walking at a cadence of >= 100 steps/minutes; for the FitBit this will be the sum of time spent "fairly active" and time spent "very active"]

Secondary exploratory physical activity outcomes:

For the activPAL:

Total time spent walking; Time sent standing; Number of sit to stand transitions; Time spent sitting; Time spent in prolonged (>=30minutes) sitting (waking hours)

For the FitBit: Distance walked; Number of floors climbed; Time spent sedentary; Time spent in light activity; Time in bed; Time asleep; Time awake; Number of awakenings; Time spent in n REM, light and deep sleep

Three types of analysis will be conducted:

(1) Feasibility of using the monitors will be established by descriptive information on the quantity (number of days worn) and quality (usable days of data) of data collected from each monitor. Descriptive information will be gathered on comfort of use and reasons for non-wear, from the feasibility questionnaire.

V3 31-08-2020

(2) The cross-sectional daily physical activity (including patterns of activity) of participants will be reported using descriptive statistics. This information will be used to characterise participants, and individual physical activity levels will be used in conjunction with interview information to develop the SUSSED framework.

(3) For people who wore both the activPAL and the Fitbit, the concurrent agreement of the primary physical outcomes outcome measures (which are assessed by both monitors) will be assessed.

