4.5.2 Questionnaires

Self reported PA levels, pain and related factors (e.g. mood, sleep, self efficacy, catastrophizing) will be measured using validated questionnaires, routinely used in clinical practice: specifically, the Brief Pain Inventory, Depression, Anxiety and Stress Scale, Pain Self-Efficacy Questionnaire (PSEQ);Pain Catastrophising Scale (PCS); Tampa Scale of Kinesiophobia and International Physical Activity Questionnaire, and the Physical Activity Stages of Change Questionnaire;. These were used in our pilot work and were straightforward to complete and acceptable to patients. The activity tracker feasibility questionnaire will also be completed at appointment 2 to capture acceptability of wearing the tracker. Questionnaires will be completed by participants in a format that best suits them (paper or over the phone). It is likely that this will be done remotely dependent on prevailing guidelines relating to COVID19 infection it may be carried out face to face following appropriate infection control measures. In this case, paper copies of the questionnaire will be included with the delivery of activity monitor/s and returned when the activity monitor/s are returned.

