4.6 TRIAL/STUDY SAFETY ASSESSMENTS

Participation in this study represents minimal risk to participants.

Participants will asked to wear an activPAL fitness tracker device continuously for one week. Such trackers have now been extensively used in research studies. The SUSSED team has considerable expertise in the use of activPAL monitors, including extended use in a frail older adult population. Acceptability of the tracker will be captured in a short survey which each participant will be asked to complete at the end of the week. If the tracker becomes uncomfortable during the week the participants will be asked to remove the tracker and contact the study team.

There is a very low risk that participants will develop a skin reaction to the materials used to attach the activPAL3 device to the thigh. The attachments to be used are all hypoallergenic and medical grade to minimize this possibility. The participants will be given a contact number of the research team to call if they have any concerns and will be told to remove the device if they encounter any skin irritation. Applicable staff and patients will be trained in appropriate removal of the waterproof dressing and monitor

Some participants will additionally be asked to wear commercially-available FitBit trackers in order to compare the accuracy of the data they collect with the data collected by the activPAL devices. Again, participants will be asked to remove these if they become uncomfortable and will complete an acceptability survey at the end of the week.

Prepaid packing will be provided for return of PA monitors. On return these will be quarantined for around one week to ensure that they are free of any active viral contamination. Trackers will be cleaned, data downloaded and reset for the next participant., Participants will complete questionnaires and interviews about their chronic pain, their general health and their levels of activity. It is possible that participants may become upset or distressed as a result of these discussions. The researcher will be fully trained to assess and support the participant and to observe whether participants are becoming emotional during certain questions. If this happens the researcher will be trained to apply care and effective communication skills to support participants in the moment. The researcher will be trained and supported by the clinical team which comprises experienced clinicians who can provide further advice on what participants may need.

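### Participant-reported monitor problems and reasons for removal are asked for only at appointment 2, so people lost before then because of the monitor go unheard and acceptability may be overstated

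*Protocol*

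**What the plan says.** Section 7.2.2.1 of the protocol lists four feasibility outcomes. One is the number of days worn. The other three are reported by the participant: problems, pain or discomfort, and the duration of and reasons for early removal or non-wear. Analysis (1) in that section has two parts:

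- The device part uses "descriptive information on the quantity (number of days worn) and quality (usable days of data) of data collected from each monitor".
- The participant part is stated as "Descriptive information will be gathered on comfort of use and reasons for non-wear, from the feasibility questionnaire".

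The timing of the questionnaire is fixed in several places. Section 4.5.2 says "The activity tracker feasibility questionnaire will also be completed at appointment 2 to capture acceptability of wearing the tracker", and section 6.1.2.2 says "Participants will be asked to complete a short questionnaire at appointment 2 to assess acceptability of wearing the trackers", adding that the researcher reads the questions out. Table 1 in section 3 gives the same time point.

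Section 4.6 covers discomfort during the week of wear. For the activPAL it says "If the tracker becomes uncomfortable during the week the participants will be asked to remove the tracker and contact the study team". It also says "Acceptability of the tracker will be captured in a short survey which each participant will be asked to complete at the end of the week". For the Fitbit it says "Again, participants will be asked to remove these if they become uncomfortable and will complete an acceptability survey at the end of the week".

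On withdrawal, section 5.5.3 says "We will request that any data collected up until the point of withdrawal be included for analysis", and that those who leave are not replaced. Section 7.3 leaves the handling of missing data to the statistical analysis plan.

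**The concern.** Acceptability of the activity measures for future studies is part of Research Question 2, and section 4.5.3 names Fitbit feasibility and acceptability as something the study will teach. The people most informative about why a monitor fails are those who give up on it. If one of them also leaves the study, or does not take part in appointment 2, the only planned occasion for asking has been missed.

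The request in 5.5.3 to keep data up to withdrawal does not help with these outcomes, because before appointment 2 none have been collected. The call described in 4.6 is the moment when the reason is known, but the protocol does not make it a source of feasibility data. A loss caused by the monitor can only lower the reported frequency of problems, so the error for such losses runs in one direction.

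**Working it through.** **Step 1. Is there another planned source?**

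- Semi-structured interview: held at appointment 1 (section 3, Table 1; section 4.4), before the week of wear.
- Study matrix (section 4.4): has no early-removal or withdrawal contact.
- Call on discomfort (section 4.6): described as a safety measure, with no record for the feasibility analysis.
- Adverse event log (section 10.2): only serious events are stated to be logged, so minor skin irritation or discomfort is not stated to be captured.
- End of study assessment (section 10.2): follows only removal or withdrawal for an adverse event, and only if required. Its content is not stated.

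No second source is described for problems, discomfort or reasons.

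**Step 2. Who is lost, and from which outcomes?**

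| Participant | Days worn, usable days | Problems, discomfort, reasons |
|---|---|---|
| Removes the monitor, stays in the study | kept | kept (survey still requested, 4.6) |
| Leaves or misses appointment 2, device returned or Fitbit account read | kept | lost |
| Leaves or misses appointment 2, activPAL not returned | lost | lost |

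**Step 3. The protocol's own figure.** Section 7.1 aims for 40 completing appointment 1 and allows 45, citing 12-15% non-attendance at routine clinics. At 12%, 40 × 1.12 = 44.8, rounded up to 45, and 40/0.88 = 45.5, rounded up to 46. At 15%, 40 × 1.15 = 46, and 40/0.85 = 47.1, rounded up to 48. The 45 therefore matches the 12% end. It is not in dispute here, and it concerns reaching appointment 1, not appointment 2.

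**Step 4. Possible size.** The protocol gives no rate of monitor-related withdrawal, so the following is an illustration. Let N be the number fitted, w the number lost before appointment 2 because of the monitor, and k the number of completers who report a problem.

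- Rate from the questionnaire: k/(N − w)
- Rate counting the w as problems: (k + w)/N
- Difference: w(N − w − k)/[N(N − w)], which is never negative

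The upper end of w borrows the 15% clinic rate as an assumption: 0.15 × 40 = 6 and 0.15 × 20 = 3. The values of k are also assumed.

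| N | k | w | k/(N − w) | (k + w)/N | Difference (points) |
|---|---|---|---|---|---|
| 40 | 4 | 0 | 4/40 = 10.0% | 4/40 = 10.0% | 0 |
| 40 | 4 | 2 | 4/38 = 10.5% | 6/40 = 15.0% | 4.5 |
| 40 | 4 | 4 | 4/36 = 11.1% | 8/40 = 20.0% | 8.9 |
| 40 | 4 | 6 | 4/34 = 11.8% | 10/40 = 25.0% | 13.2 |
| 20 (Fitbit) | 2 | 1 | 2/19 = 10.5% | 3/20 = 15.0% | 4.5 |
| 20 (Fitbit) | 2 | 3 | 2/17 = 11.8% | 5/20 = 25.0% | 13.2 |

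Varying k from 2 to 8 of 40, or from 1 to 4 of 20, with w in the same ranges, gives a difference between 0 and about 14 points.

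**Step 5. Losses for other reasons.** If 6 of 40 were lost for unrelated reasons and had no monitor problem, the questionnaire would give 4/34 = 11.8% against 4/40 = 10.0%. Problems would then be slightly overstated. The one-directional argument applies only to losses caused by the monitor.

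**The case against.** The strongest reply is that the protocol already expects people to take a monitor off and still report why. Section 4.6 asks every participant for the survey and says that those who remove the Fitbit will complete it, and early removal of the activPAL is itself a listed outcome. That stands. A reader might infer that the plan confuses stopping a monitor with leaving the study, and the text does not support that.

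A reader might also infer that people who withdraw vanish from the whole feasibility result. They do not: days worn and usable days come from the device, and 5.5.3 seeks to keep data collected up to withdrawal.

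Third, the loss may be small or absent. Section 7.1 expects no high dropout, section 4.5.3 reports good activPAL compliance in patients with moderate to severe pain, and the study team contacts participants for appointment 2 within a window of 7-11 days. The 12-15% is a routine-clinic rate, and treating every loss as caused by the monitor is a worst case. This also stands, and it is why the table starts at zero.

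Fourth, denominators and missing-data rules belong to the statistical analysis plan, which is not at hand, and the protocol states no completers-only denominator. That is right as far as it goes. But an analysis plan can only choose how to count people. It cannot supply reasons that nobody asked for, and the time of asking is set in the protocol.

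Finally, the study is exploratory and descriptive, and the protocol sets no acceptability threshold. That limits the consequences without removing the gap.

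**Conclusion.** The point holds in a limited form. The three participant-reported feasibility outcomes have one stated collection point, and anyone lost before it because of the monitor contributes nothing to them. For those outcomes, acceptability may be overstated. The monitor-based outcomes are not affected if the device is returned or the account is read.

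The firmer conclusion, that acceptability will be overstated by a known amount, is not supported. The number of monitor-related losses is not given and may be zero, in which case this bias is zero. The difference of 0 to about 14 points rests on assumed values of w and k, with the upper end taken from a clinic non-attendance rate and every loss attributed to the monitor. This is a cheap improvement to data collection. It is not an internal contradiction or an error in a stated figure.

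**What to change.** - **Sections 4.5.2, 4.6 and 5.5.3:** state that the existing brief feasibility questions, including the reason for stopping, will be asked at any early-removal call or withdrawal contact as well as at appointment 2. Answering after withdrawal should be voluntary.
- **Section 7.2.2.1, analysis (1):** state that these answers will be used, and that those who stop before appointment 2 will be shown separately with the reason where given. The exact denominator can stay with the statistical analysis plan.

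The cost is a few sentences and one extra use of a short questionnaire that already exists, for the activPAL often on a call that section 4.6 already asks for. Some people who withdraw will decline to answer, and the feasibility figures may look slightly less favourable.

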7.2.2.2 Validated questionnaires

Information from the questionnaires will be used to inform the SUSSED framework. Questionnaire data will also be compared with data collected by the Fitness trackers.

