4.4 TRIAL/STUDY MATRIX

Population 1 (patients referred to Tayside Pain Service)

	Initial telephone contact	Study Appointment 1 (Face to face or remote contact)	Study Appointment 2 (7-11 days after Study Appointment 1)* (face to face or remote contact)
Eligibility	х		
Consent	х		
Semi structured interview		Х	
Questionnaires		x	x
Demographics		x	
Fitness tracker fitted		x	
Fitness tracker removed			х

V3 31-08-2020

*All best efforts will be made to ensure that participants have this second appointment one week after study appointment 1. However, if this appointment takes place up to 4 days beyond 1 week (e.g. to reduce burden on participant/ avoid weekends/ Public holidays for appointments) this will not constitute a breach of protocol.

Population 2 (stakeholders such as healthcare professionals, members of relevant community organisations and leisure centre staff)

	Study appointment 1 (Face to face or remote contact)
Eligibility	х
Consent	х
Semi structured interview	Х

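### The protocol gives two end points for monitor wear, so a late second appointment can leave part of the activity questionnaire's recall week unmonitored

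*Protocol*

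**What the plan says.** Section 7.2.2.2 plans the comparison in one sentence: "Questionnaire data will also be compared with data collected by the Fitness trackers". It does not name the questionnaire occasion or the monitored days.

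Section 6.1.2.1 gives the self-report activity measure as the "International Physical Activity Questionnaire (short form, last 7 days" version, and on timing says "Validated questionnaires will be completed by participants at study appointments 1 and 2".

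On wear, section 6.1.2.2 has participants "instructed on how to fit the activPAL monitor at study appointment 1 and advised to wear this continuously for seven days". Sections 4.2, 4.5.3 and 4.6 also speak of one week. The next sentence of 6.1.2.2 reads "At the second, remote study appointment they will be instructed how to remove the trackers", and the matrix in section 4.4 likewise puts tracker removal at appointment 2.

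That appointment is aimed at one week, but the footnote to 4.4 says there is no breach "if this appointment takes place up to 4 days beyond 1 week". Both the matrix and the flowchart in 4.3 give the window as 7 to 11 days.

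**The concern.** Wear ends either seven days after fitting or at appointment 2. For a visit on days 8 to 11 these are different instructions, and a participant can follow only one of them.

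The choice affects two planned outputs.

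- **Questionnaire against tracker.** Section 4.2 says that collecting several sources of data allows their concurrent validity to be judged, to guide outcome measurement in later trials. If the recall week and the monitored week cover different days, real day-to-day variation in activity adds to the disagreement between the measures. It cannot then be separated from reporting error.
- **Feasibility of wear.** Section 7.2.2.1 counts the days each monitor was worn and asks about early removal of the activPAL. Early has no fixed meaning while planned removal is both day 7 and the visit day. If wear runs to the visit, the count rises with the appointment date whatever the participant's tolerance of the device.

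**Working it through.** **Inputs, all from the protocol**

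- Fitting: appointment 1, taken as day 0 (4.4, 6.1.2.2).
- Recall: the 7 days before the IPAQ is completed (6.1.2.1).
- Appointment 2: day d, with d from 7 to 11 (4.3, 4.4).
- End of wear: day 7 (reading A, the seven-day advice in 6.1.2.2) or day d (reading B, removal at appointment 2 in 4.4 and 6.1.2.2).

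**The plan's own figure.** One week plus the permitted 4 days is 7 + 4 = 11 days, which reproduces the upper limit of the window. The protocol states no overlap figure.

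**Formula.** With the form completed on day d, the recall interval is d − 7 to d.

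- Reading A: wear is 0 to 7, so overlap = 7 − (d − 7) = 14 − d.
- Reading B: wear is 0 to d and contains the whole recall interval, so overlap = 7. Days recorded before the recall interval = d − 7.

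| Appointment 2 on day | A: recalled days monitored | B: recalled days monitored | B: days recorded | B: recorded before recall week |
|---|---|---|---|---|
| 7 | 7 of 7 (100%) | 7 of 7 | 7 | 0 |
| 8 | 6 of 7 (86%) | 7 of 7 | 8 | 1 |
| 9 | 5 of 7 (71%) | 7 of 7 | 9 | 2 |
| 10 | 4 of 7 (57%) | 7 of 7 | 10 | 3 |
| 11 | 3 of 7 (43%) | 7 of 7 | 11 | 4 |

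These are elapsed 24-hour days. In calendar days, the day-11 case under reading A is three full days plus part of a fourth.

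**What analysis can and cannot repair.** Under B the surplus days can be dropped, because section 4.2 describes activPAL data with timing and daily Fitbit records. Under A the recalled days after day 7 were never recorded, so a later choice of days cannot restore them.

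**The case against.** The strongest reply is that the plan works as intended. Section 4.4 commits to best efforts for a one-week appointment, and on day 7 the recall week and the monitored week coincide. If wear runs to the visit, overlap is complete at every permitted visit. The figure of 3 of 7 needs both a day-11 visit and wear stopped at day 7. The only agreement analysis set out in detail, activPAL against Fitbit in 7.2.2.1, does not involve the questionnaire. The study is exploratory, and section 7.2 leaves specific analyses to the SAP. All of this stands, and it limits the size of the point. It does not remove the conflict over when wear ends, which is fixed at data collection.

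A reader might go further in four ways that the document does not support.

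- **That the comparison covers different days in general.** It does not: overlap is complete on day 7, and on any permitted day if wear runs to the visit.
- **That the appointment 1 IPAQ, whose recall week precedes fitting, will be set against the tracker.** The protocol never says so, and the choice of occasion is ordinary SAP content.
- **That paper forms are completed late or kept by the participant.** Section 4.5.2 does have remote paper copies "returned when the activity monitor/s are returned". However, 6.1.2.1 also offers freepost return or reading the questions aloud, and it places completion at the appointments.
- **That every questionnaire is affected.** Only the IPAQ has a stated seven-day window.

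**Conclusion.** The protocol contradicts itself on when monitor wear ends for any appointment 2 after day 7. If participants follow the seven-day advice, a late visit leaves 6, 5, 4 or 3 of the 7 recalled days monitored (86% down to 43%), and the loss cannot be recovered. If they wear the monitor until the visit, nothing is lost for the comparison, but 1 to 4 extra days are recorded and the count of days worn partly measures scheduling.

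This assumes that the IPAQ is completed on the day of appointment 2 and that the monitor is fitted at appointment 1. The protocol gives no expected share of late visits, so the number of participants affected among the planned 40 is unknown; with all visits on day 7 it would be none. The point is confined to the IPAQ comparison and the wear outcome. It is worth correcting before data collection because the SAP cannot supply unrecorded days.

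**What to change.** 1. Reconcile sections 4.4 and 6.1.2.2 so that one end of wear is stated for visits on days 8 to 11, and bring the one-week statements in 4.2, 4.5.3 and 4.6 into line.
2. Align the appointment 2 IPAQ with the monitored week. Either have it completed and dated at the end of the seven-day wear even if the call is later, or continue wear until appointment 2. Each gives 7 of 7 recalled days for any visit from day 7 to day 11.
3. State in 7.2.2.2 that the IPAQ comparison uses the appointment 2 form and only the monitored days that it recalls.
4. In 7.2.2.1, report days worn against a fixed seven-day denominator, so that a later appointment cannot raise the count, and define early removal against the same end point.

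The cost is a few sentences, a date line on the form and a protocol amendment. Section 12.1 requires approval from the Sponsor, the REC and NHS R&D before it takes effect. Sample size and number of appointments do not change.
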